13.5 Vital signs

In CRS-1 and CRS-2 no vital signs information was collected.

Vital sign measurements include heart rate (HR), systolic and diastolic blood pressure (BP), respiratory rate. Actual values and change from baseline for each parameter at baseline and per follow-up visit will be summarized with descriptive statistics.

Additionally, potentially clinically significant vital signs will be identified for selected parameters as defined below. These abnormalities will be summarized using shift tables at baseline and per follow-up visit.

- Systolic BP: <90 mmHg, normal, >140 mmHg 160 mmHg, >160 mmHg
- Diastolic BP: <50 mmHg, normal, >90 mmHg 100 mmHg, >100 mmHg
- HR: <60 beats per minute (bpm), normal, >100 bpm.

Listings: It will be provided a listing with date of visit, visit type (baseline, follow-up month or unscheduled), supine systolic blood pressure (mmHg), supine diastolic blood pressure (mmHg), supine heart rate (beats per minute) and supine respiratory rate (breaths per minute), order by center, patient identification and date of visit.

13.6 Physical examination

In CRS-1 and CRS-2 no physical examination information was collected.

Listings: It will be provided a listing with date of visit, visit type (baseline, follow-up month or unscheduled), height and weight order by center, patient identification and date of visit.

13.7 Fundoscopic examination

In CRS-1 and CRS-2 no funduscopic examination information was collected.

The funduscopic examinations will be classified as Normal, Abnormal NCS or Abnormal CS for Examination findings. Data will be summarized by visit using shift tables.

Listings: It will be provided a listing with date of visit, visit type (baseline, follow-up month or unscheduled), left eye fundoscopic exam normal/abnormal, left eye examination findings, right eye fundoscopic exam normal/abnormal and right eye examination findings, order by center, patient identification and date of visit.

13.8 Other safety variables

No other safety data are to be analysed.

V1.0 07 June 2021

14 Deviations from the analyses planned in the current study protocol

There are currently no deviations from the CRS-1 CSP (version 1), CRS-2 CSP (version 1.0) and SNT-IV-005 CSP version 3.0 dated 06 March 2019 and SNT-IV-005 CSP addendum COVID-19 version1.0 dated 29 May 2020

15 Data analysis procedures

Statistical data analysis will be performed by 4Pharma Ltd according to current SAP.

Statistical analysis, tables and patient data listings will be performed with SAS® version 9.4 or higher for Windows (SAS Institute Inc., Cary, NC, USA).

16 Definitions

2nd eye onset

Most recent affected eye at Baseline.

Baseline (BL)

LEROS BL

NH BL

Best Visual Acuity

VA of the eye with best logMAR at the visit. However, if both eyes are off-chart, regardless of the VA, both eyes are considered as best eye.

Note: best eye at BL may not be the same as best eye at 6, 18 and 24 months or last assessment.

Clinical Relevant Benefit (CRB)

Defined as the composite of CRR and CRS, i.e, if the eye/patient has a CRR and/or a CRS then the eye/patient has also a CRB.

Clinical Relevant Recovery (CRR)

CRR is defined as improvement

or

- from "off-chart" (the equivalent of CF, HM, LP or NLP) VA to at least 1.6 logMAR value
 - of at least 0.2 logMAR value within "on-chart". Clinical Relevant Stabilization (CRS)

Is defined as maintenance of VA <1.0 logMAR in eyes with VA <1.0 logMAR at BL.

Clinical Relevant Worsening (CRW)

For any "on-chart" VA, CRW is defined as the disability to read at least 10 additional letters (equivalent to two chart lines) or a worsening to off-chart values (the equivalent of CF, HM, LP or NLP).

SNT-IV-005 Statistical Analysis Plan

Confidential

Delta onset

Is the time between symptoms onset of both eyes: date 2nd symptoms onset – date 1st symptoms onset. Patients will not be considered for calculating Delta onset if only one eye is affected or both eyes have the same date of symptom onset.

Months in Treatment

Months in treatment is only applied to LEROS patients. It is defined as time since BL to last follow-up during treatment period.

Nadir

Is the defined when VA reaches its worst point (highest logMAR or off-chart value). Time of nadir is the first time that nadir is reached.

Off-Chart

It is considered off-chart any VA entered as

- CF, HM, LP or NLP
- Any value above 1.68 logMAR

Patients ≤1 year after the onset of symptoms

A patient is considered ≤ 1 year after the onset of symptoms if, at BL, the most recent affected eye is ≤ 1 year after the onset of symptoms at BL for that eye.

Patients >1 year after the onset of symptoms

A patient is considered >1 year after the onset of symptoms if, at BL, the most recent affected eye is >1 year after the onset of symptoms at BL for that eye.

TEAE (Treatment Emergent Adverse Events)

TEAE that starts after the patient receives the first dose of study treatment.

Time in treatment at CRR by follow-up

Time in treatment at follow-up is divided in 5 categories:

- Before 6 months follow-up
- After 6 months follow-up up to 12 months follow-up
- After 12 months follow-up up to 18 months follow-up
- After 18 months follow-up up to 24 months follow-up

Visual Acuity blindness categories

VA categories are defined as follow:

- Non-legally blind: logMAR < 1.0;
- Legally blind: $1.0 \le logMAR \le 1.68$
- Off-chart: CF, HM, LP or NLP

17 Data derivations and imputation rules

17.1 LEROS

Date of Birth:

- If month missing then 01JUL
- If Day missing (always) then 1st day of month

Onset date

- Day missing: 1st of the month
- Month missing: 1st of July

Idebenone start/stop, AE onset/stop date:

All dates are complete

Concomitant medication / Medical History start date:

Day missing: 1st of month

Month missing: January

Year missing: Set null

Concomitant medication / Medical History end date:

Day missing: last day of month

Month missing: December

Year missing: Set null

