8.4 Natural History control set

The Natural History (NH) external control set for LEROS study is constituted by the combined data from CRS-1 and CRS-2. In order to ensure comparability between populations, the following criteria, based on LEROS inclusion/exclusion (section 5.4 and 5.5) criteria and patients included in the ITT population, are required for subjects to be included in the external NH (Natural History) control set out of all patients included in CRS-1 and CRS-2:

SNT-IV-005 Statistical Analysis Plan

Confidential

- Carriers of only one of the three major LHON mtDNA (G11778A, G3460A or T14484C)
- Age \geq 12 years;
- No other cause of visual impairment apart from LHON;
- Date of symptoms onset is defined (or at least month and year known);
- Onset of symptoms are less or equal to 5 years at BL visit;
- At least 2 VA assessments;
- VA assessments visit date must be defined (or at least month and year known).

The NH control set in conjunction with the ITT population will be used to evaluate efficacy endpoints defined in section 4.

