8.5.1 Matching algorithm for the primary endpoint

The external NH control set for the eyes with BL \leq 1 year since onset of symptoms in the LEROS ITT population will be generated as follows (section 19.1 presents the matching algorithms using workflow diagrams and provides examples of matched BL and follow-up visits):

1. Since there is no treatment to be considered in the NH control set, in principle any VA observation at any time point after the onset of symptoms in any eye can be used as a BL for that eye. The primary outcome measure in LEROS is the VA at 12 months after BL. Therefore, using a "window" of ±3 months, any eye with a VA observation at any time point in the NH control set which has a follow-up VA assessment within

SNT-IV-005 Statistical Analysis Plan

Confidential

12±3 months will be retained for use as a possible BL observation. All such possible BL observations and subsequent VA assessments will form the NH control subset to be compared to the BL of LEROS.

- 2. In LEROS, the average time from the onset of symptoms to the start of Raxone® treatment will be calculated once all data is available. The start of the Raxone® treatment will be used as the BL in the statistical analyses.
- 3. For each VA observation retained in the NH control subset, the time from the onset of symptoms at each possible BL time point will be calculated for each eye.
- 4. For each eye in the NH control subset, the VA observation for which time since onset of symptoms is closest to the average time since onset of symptoms at BL calculated for LEROS (see 2) will be selected as the BL VA observation for that eye. Any eye in the NH control subset with a BL VA observation >6 months after the average time since onset of symptoms at BL in LEROS will be discarded. The resulting dataset will form the "final NH control subset" to be used for the primary endpoint. In this way, BL observations in the final NH control subset will be closely matched to the BL in the LEROS ITT population.
- 5. The change from BL in VA at 12±3 months for each eye in the final matched NH control subset will be compared to the change from BL visit to the visit scheduled at Month 12 in LEROS.

This algorithm will guarantee that the time from the onset of symptoms to the BL assessment is comparable between the final NH control dataset and LEROS.

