12.1 Primary endpoint

Endpoint: Proportion of eyes with clinically relevant recovery (CRR) of visual acuity from Baseline (BL) or in which BL VA better than 1.0 logMAR was maintained at Month 12 in patients treated with Raxone® ≤1 year after the onset of symptoms, compared to matching external natural history control group. CRR definition is presented in section 16.

Analysis sets: Primary endpoint analysis will use all LEROS mITT eyes that are ≤1 year since onset of symptoms at BL and have the Month 12 assessment. External NH control set is generated as described in section 8.5.1 (Matching algorithm for the primary endpoint), using VA assessments within 12±3 months from BL.

Analysis method: The primary endpoint will be analysed using a logistic regression model. The binary response will be used as the dependent variable. The independent variables include the treatment group (Raxone® treated patients versus untreated control group), gender (male, female) and mutation group (G11778A, G3460A, T14484C) as fixed factors.

The difference between the Raxone® treated patients versus NH group will be estimated with odds ratio, two-sided 95% confidence intervals and two-sided p-values

```
proc logistic;
  class treatment gender mutation / param=ref;
  model CRB(event='1') = treatment mutation gender / link=logit clodds=pl;
  oddsratio treatment;
run;
```

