17.2 Natural History

17.2.1 Dates imputations

Idebenone start date

- Day missing
 - if there is a VA visit in the same month, then date of the visit
 - otherwise, 1st day of the month
- Month missing: 01 January
- Year missing: 01 January 1900

Idebenone stop date

- Day missing: last day of the month (28 for February)
- Month missing: 31 December
- Year missing; null

Onset date

- Day missing: 15th of the month
- Month missing: 1st of July

Visit date

- Day missing: 15th day of the month
- Month missing: 01 July
- Year missing: null

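### A missing onset day is set to the 1st of the month in LEROS but the 15th in the controls, and the exact CRR limits have no rounding rule: a small, avoidable difference between arms.

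*SAP*

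**What the plan says.** **Onset dates.** For LEROS, SAP 17.1 gives "Day missing: 1st of the month" and "Month missing: 1st of July". For the natural history data, SAP 17.2.1 gives "Day missing: 15th of the month", and also 1 July when the month is missing. The month rule cannot reach controls in the comparison, because SAP 8.4 admits them only if "Date of symptoms onset is defined (or at least month and year known". Neither the LEROS entry criteria, nor the ITT and mITT definitions, nor 17.1 states such a condition for LEROS eyes. Section 17.2.1 does have a same-month rule, but for idebenone start: "if there is a VA visit in the same month, then date of the visit".

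**Use of the onset date.** SAP 8.5.1 selects each control eye's baseline as the observation whose time since onset is "closest to the average time since onset of symptoms at BL calculated for LEROS", and then states: "This algorithm will guarantee that the time from the onset of symptoms to the BL assessment is comparable". SAP 12.1 takes into the primary analysis the mITT eyes that are at most 1 year "since onset of symptoms at BL and have the Month 12 assessment". Time since onset also enters the propensity score in 12.1.1, which is a sensitivity analysis.

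**Response limits.** SAP 16 sets CRR at 1.6 logMAR or better from off-chart, or a gain of 0.2 logMAR or more on-chart. SAP 17.2.2 converts CRS-2 acuities that lack logMAR by the negative base-10 logarithm of the decimal value and states no rounding. Protocol 9.2.1 describes the same limits as one full chart line (five letters) and two lines (ten letters).

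**The concern.** With an external control, the comparison depends on deriving the matching variable in the same way in both sources. Here a written rule derives it differently, and no reason is given. In LEROS the 1st-of-month rule errs in one direction only: time since onset is overstated, and an eye can leave the ≤1-year set but not enter it. The 1 July rule for an unknown month is much coarser and, within the matched comparison, can act only on LEROS eyes.

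The missing rounding rule acts on the binary response itself. Two programmers could both follow the SAP and classify the same eye differently. A rounding rule chosen after the data are seen would be open to challenge.

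**Working it through.** The plan gives no figure on this point, so there is none to reproduce. The numbers of missing days, missing months and converted acuities are not given either, so results are shown per affected eye or as a range.

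**1. Day rule**
- Mean day of the month over a 365-day year: (7 × 496 + 4 × 465 + 406) / 365 = 5738 / 365 = 15.72.
- Mean overstatement of time since onset: 15.72 − 1 = 14.72 days (LEROS rule) and 15.72 − 15 = 0.72 day (control rule).
- Offset: 14.0 days; 14 / 30.4375 = 0.46 month.
- Shift of the LEROS mean, relative to using the 15th: 0.25 × 0.46 = 0.12 month at 25% missing, and 0.50 × 0.46 = 0.23 month at 50%. The ceiling, with every day missing, is 0.46 month.

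**2. The 1-year cut.** Assumption: true onset uniform over the year before baseline, enumerated over 365 baseline dates. The entry for onset truly 1–2 years earlier uses onset 366–730 days before baseline.

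| Rule | Pushed past 1 year | Onset after baseline | Truly 1–2 years, classed ≤1 year |
|---|---|---|---|
| 1st of month | 4.02% | 0% | 0% |
| 15th of month | 1.14% | 0.94% | 0.95% |
| 1 July (month unknown) | 12.60% | 12.33% | 12.36% |

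Percentages are of affected eyes only. Applied to the 110 evaluable LEROS eyes of SAP 6, the 1st rule moves out 110 × 4.02% × 0.25 = 1.1 eyes at 25% missing and 2.2 at 50%. The 15th rule moves out 110 × 1.14% × 0.25 = 0.3 and 0.6. With the 15th plus a same-month guard, onset after baseline falls to 0% and the mean overstatement is 0.77 day.

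**3. Response limits.** Assumption: log-spaced Snellen lines.
- Off-chart to 20/800: −log10(20/800) = 1.602, which is worse than 1.6, so no CRR on a literal reading.
- Two-line gains from a baseline of 1.0 or worse: 20/630 to 20/400 = 0.197; 20/500 to 20/320 = 0.194; 20/250 to 20/160 = 0.194. These 3 of 7 fall below 0.2. Short gains that start and stay better than 1.0 still count in the primary endpoint through the stabilization component.
- If LEROS logMAR values on the 0.02 letter grid are subtracted in unrounded double precision, 24 of 35 gains of exactly ten letters from baselines 1.00 to 1.68 compute just below 0.2 (1.68 − 1.48 is stored as 0.19999999999999996). Either arm can therefore lose responders.
- Rounding each value to two decimals and then the difference: 20/800 becomes 1.60, and the three gains above become 1.50 − 1.30, 1.40 − 1.20 and 1.10 − 0.90, each 0.20. Decimal 0.032 to 0.05 becomes 1.49 − 1.30 = 0.19 and still fails.

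**The case against.** The strongest reply is that the date effect is negligible. A shift of 0.12 to 0.23 month is small against the ±3-month follow-up window and the 6-month discard rule, and 0.46 month would require every LEROS onset day to be missing, for which the text gives no support. That stands: this is a consistency fault, not a demonstrated bias.

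Three further replies stand in part.
- For controls, step 1 of 8.5.1 already limits candidate baselines to acuities after onset, so an imputed control onset that falls after a visit is largely dealt with.
- No document shows that any LEROS eye has an unknown onset month. Enrolment by time-since-onset stratum makes it unlikely near the 1-year cut, and the selection figures in SAP 19.1 are not legible here, so a guard shown there cannot be ruled out.
- The ten-letter wording of the protocol could be said to settle LEROS scores, since SAP 14 declares no deviations. It does not settle converted Snellen or decimal control values.

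A reader might infer that a definite number of control eyes would change baseline. The documents do not support this: SAP 8.4 requires only two assessments, an eye with one qualifying baseline cannot switch, and a different baseline need not change the response. A reader might also infer that the primary odds ratio shifts by a known amount or favours one arm. Nothing in the documents gives the number of eyes at the limits, and losses are possible in both arms.

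**Conclusion.** The point holds as a minor to moderate specification fault that should be corrected. The 14-day offset between arms follows directly from the two written rules. Its effect on the LEROS mean depends on the unknown share of missing days. The movement across the 1-year cut also rests on the assumed uniform onset and amounts to about one or two eyes at 25% to 50% missing. The word guarantee in 8.5.1 is too strong while the input is derived differently by arm.

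The unknown-month rule could do more harm per eye, but it matters only if such eyes exist. The rounding gap is real on a literal reading and bears on the primary response. Its size and direction cannot be derived from the documents, and the Snellen examples assume log-spaced lines.

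**What to change.** **Onset date**
- Use the 15th for a missing onset day in both arms.
- In LEROS, if the imputed onset falls after baseline in the same calendar month, use the baseline date. For controls, step 1 of 8.5.1 already applies.
- For any LEROS eye with an unknown onset month, apply the month-and-year-known condition of 8.4 in the matched comparison, and add a sensitivity analysis that keeps those eyes.

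**Response limits**
- Before testing the 1.6, 0.2, 1.0 and 1.68 limits, apply one rounding rule to observed and converted values in both arms. Fix it before database lock and check it against the Snellen and decimal steps actually recorded. Two decimals on the values and then on the difference handles the standard Snellen lines but not decimal 0.032 to 0.05.
- State explicitly how the multiply imputed LEROS values of 12.1.1 are tested against the limits.

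**Reporting.** Give by arm the number of imputed onset dates and of converted acuities.

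**Cost.** A few lines in SAP 17 and in the derivation program, plus one sensitivity analysis. A few LEROS eyes may leave the matched comparison, and the response rate of either arm may rise slightly.

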17.2 Natural History

17.2.1 Dates imputations

Idebenone start date

- Day missing
 - if there is a VA visit in the same month, then date of the visit
 - otherwise, 1st day of the month
- Month missing: 01 January
- Year missing: 01 January 1900

Idebenone stop date

- Day missing: last day of the month (28 for February)
- Month missing: 31 December
- Year missing; null

Onset date

- Day missing: 15th of the month
- Month missing: 1st of July

Visit date

- Day missing: 15th day of the month
- Month missing: 01 July
- Year missing: null

17.2.2 Visual Acuity Derivation

For visual acuity in CRS-1 it should be used the variable logmar.

CRS-2 logMAR values may not be available, therefore, a conversion it is necessary.

Conversion from decimal to logMAR: -log10(decimal)

Snellen to decimal: VASSNEL1 / VASSNEL2

Off-chart values to logMAR:

• CF: 2 logMAR

• HM: 2.3 logMAR

• LP: 2.6 loMAR

• NLP: 2.9 logMAR

18 References

European Medicines Agency: Guideline on Data Monitoring Committees. London 2007; EMEA/CHMP/EWP/5872/

Study: SNT-IV-005

19 Appendices

19.1 Matching algorithm workflow

Figure 19.1.1- LEROS eyes selection algorithm

[figure not shown]
[figure not shown]

[figure not shown]
Figure 19.1.2 - Natural History eyes selection algorithm

[figure not shown]

19.1.1 Natural History matching control pair selection example

[figure not shown]
Natural History subject A

[figure not shown]
Natural History subject B

Natural History subject C

Natural History subject D

19.2 Table shell structure

Table 19-1 - Table shell for the comparison between LEROS and NH control group

Table Description	LEROS matched ITT	NH matched
Categorical variable, N	xx	xx
Category 1 n (%)	xx (xx.x%)	xx (xx.x%)
Category 2 n (%)	xx (xx.x%)	xx (xx.x%)
	xx (xx.x%)	xx (xx.x%)
Continuos variable, N	xx	xx
mean (SD ; SE)	xx.xx (xx.xx ; xx.xx)	xx.xx (xx.xx ; xx.xx)
median (Q ₁ – Q ₃)	xx.xx (xx.xx – xx.xx)	xx.xx (xx.xx – xx.xx)
min-max	xx.xx - xx.xx	xx.xx – xx.xx

Table 19-2 - Table shell for LEROS ITT population

Table Description	2 nd eye onset ≤ 1 year	2 nd eye onset > 1 year	LEROS ITT
Categorical variable, N	xx	xx	xx
Category 1 n (%)	xx (xx.x%)	xx (xx.x%)	xx (xx.x%)
Category 2 n (%)	xx (xx.x%)	xx (xx.x%)	xx (xx.x%)
	xx (xx.x%)	xx (xx.x%)	xx (xx.x%)
Continuos variable, N	xx	xx	xx
mean (SD ; SE)	xx.xx (xx.xx ; xx.xx)	xx.xx (xx.xx ; xx.xx)	xx.xx (xx.xx ; xx.xx)
median (Q₁ – Q₃)	xx.xx (xx.xx – xx.xx)	xx.xx (xx.xx – xx.xx)	xx.xx (xx.xx – xx.xx)
min-max	xx.xx - xx.xx	xx.xx – xx.xx	xx.xx – xx.xx

Table 19-3 - Table shell for primary LHON mtDNA mutations subgroup analysis

Table Description	G11778A	G3460A	T14484C	Other Mutation
Categorical variable, N	xx	XX	xx	xx
Category 1 n (%)	xx (xx.x%)	xx (xx.x%)	xx (xx.x%)	xx (xx.x%)
Category 2 n (%)	xx (xx.x%)	xx (xx.x%)	xx (xx.x%)	xx (xx.x%)
•••	xx (xx.x%)	xx (xx.x%)	xx (xx.x%)	xx (xx.x%)
Continuos variable, N	xx	xx	xx	xx
mean (SD; SE)	xx.xx (xx.xx ; xx.xx)			
median $(Q_1 - Q_3)$	xx.xx (xx.xx – xx.xx)	xx.xx (xx.xx – xx.xx)	xx.xx (xx.xx – xx.xx)	xx.xx (xx.xx – xx.xx
min-max	xx.xx - xx.xx	xx.xx – xx.xx	xx.xx – xx.xx	xx.xx – xx.xx

Table 19-4 - Table shell for age at baseline subgroup analysis

Table Description	< 18 years	≥ 18 and < 35 years	≥ 35 years
Categorical variable, N	xx	xx	xx
Category 1 n (%)	xx (xx.x%)	xx (xx.x%)	xx (xx.x%)
Category 2 n (%)	xx (xx.x%)	xx (xx.x%)	xx (xx.x%)
•••	xx (xx.x%)	xx (xx.x%)	xx (xx.x%)
Continuous variable, N	xx	xx	xx
mean (SD; SE)	xx.xx (xx.xx ; xx.xx)	xx.xx (xx.xx ; xx.xx)	xx.xx (xx.xx ; xx.xx)
median (Q ₁ – Q ₃)	xx.xx (xx.xx – xx.xx)	xx.xx (xx.xx – xx.xx)	xx.xx (xx.xx – xx.xx)
min-max	xx.xx – xx.xx	xx.xx - xx.xx	xx.xx – xx.xx

Table 19-5 - Table shell for Blindness Category of Best VA at BL subgroup analysis

Table Description	Off-chart	Legally blind	Non-legally blind
Categorical variable, N	xx	xx	xx
Category 1 n (%)	xx (xx.x%)	xx (xx.x%)	xx (xx.x%)
Category 2 n (%)	xx (xx.x%)	xx (xx.x%)	xx (xx.x%)
•••	xx (xx.x%)	xx (xx.x%)	xx (xx.x%)
Continuos variable, N	xx	xx	хх
mean (SD ; SE)	xx.xx (xx.xx; xx.xx)	xx.xx (xx.xx ; xx.xx)	xx.xx (xx.xx ; xx.xx)
median (Q ₁ – Q ₃)	xx.xx (xx.xx – xx.xx)	xx.xx (xx.xx – xx.xx)	xx.xx (xx.xx – xx.xx)
min-max	xx.xx - xx.xx	xx.xx – xx.xx	xx.xx – xx.xx

Table 19-6 - Table shell for Safety population

Table Description	Safety Population
Categorical variable, N	xx
Category 1 n (%)	xx (xx.x%)
Category 2 n (%)	xx (xx.x%)
	xx (xx.x%)
Continuos variable, N	xx
mean (SD ; SE)	xx.xx (xx.xx ; xx.xx)
median (Q₁ – Q₃)	xx.xx (xx.xx – xx.xx)
min-max	xx.xx - xx.xx

Table 19-7 - Table shell for Survival Analysis using Kaplan-Meier method

Variable in analysis	6 months	12 months	18 months	24 months	Last Visit*
ITT patients	,		,		
At risk, n (%) ¹	xx (xx.x%)				
Event, n (%) ¹	xx (xx.x%)				
Censored, n (%) ¹	xx (xx.x%)				
KM, [95%CI] ²	xx.x% [xx.x,xx.x]				
RKM, [95%CI] ³	xx.x% [xx.x,xx.x]				
SE ⁴	xx.x	xx.x	xx.x	xx.x	xx.x
Subgroup 1					
At risk, n (%) ¹	xx (xx.x%)				
Event, n (%) ¹	xx (xx.x%)				
Censored, n (%) ¹	xx (xx.x%)				
KM, [95%CI] ²	xx.x% [xx.x,xx.x]				
RKM, [95%CI] ³	xx.x% [xx.x,xx.x]				
SE ⁴	xx.x	xx.x	xx.x	xx.x	xx.x
Subgroup					l.
At risk, n (%) ¹	xx (xx.x%)				
Event, n (%) ¹	xx (xx.x%)				
Censored, n (%) ¹	xx (xx.x%)				
KM, [95%CI] ²	xx.x% [xx.x,xx.x]				
RKM, [95%CI] ³	xx.x% [xx.x,xx.x]				
SE ⁴	XX.X	xx.x	xx.x	xx.x	xx.x

¹ n (%) values are presented as frequency and percentages; ² KM: Kaplan-Meier estimate; ³ RKM: Reverse Kaplan-Meier estimate; ⁴ SE: Standard Error

Study: SNT-IV-005

V1.0 07 June 2021
